1 PROTOCOL SUMMARY

1.1 SYNOPSIS

Title:	MASLIHAT Intervention for Tajik Male Migrants Who Inject Drugs
Grant Number:	1R01DA050464
Study Description:	
This protocol will test the efficacy of the MASLIHAT peer education HIV prevention intervention for Tajik migrant laborers who inject drugs in the host country, against an attention control. The primary outcomes are self-reported risk behaviors among participants and network members over 12 months following the intervention, including syringe sharing, and sex without condom. Follow-up interviews will be conducted at 3, 6, 9, and 12 months. We will conduct HIV testing at baseline and 12-month follow-up, and HCV testing at baseline and 6- and 12-month follow-up. We expect the MASLIHAT intervention to be associated with greater reduction in injection and sexual risk behavior during follow-up compared with the control condition.

Objectives[*]:	
Primary Objective: Assess the efficacy of the MASLIHAT intervention compared to the TANSIHAT control condition for reducing injection equipment sharing, condomless sex, and heavy alcohol use among intervention participants and among their network members.
 
Secondary Objectives: Assess the efficacy of the MASLIHAT intervention compared to the TANSIHAT control condition for reducing the incidence of HIV and hepatitis C infection among intervention participants and among their network members

Endpoints[*]:	
Primary Endpoint: Reduce the proportion of men sharing syringes or other injection equipment in the past 3 months to 10% or less; reduce the proportion of men engaging in condomless sex in the past 3 months to 10% or less. Reduce the proportion of men engaging in heavy alcohol use in the past 3 months to 10% or less.
 
Secondary Endpoints: Reduce the 12-month incidence of HIV and HCV by 50% compared to the control group.
 
We will enroll a total of 420 male Tajik migrant workers who inject drugs in Moscow, including 140 intervention participants (70 MASLIHAT, 70 control group) and 280 network members recruited by the intervention participants for participation in the assessments.

Phase[*] or Stage:	Phase 2
Description of Sites/Facilities Enrolling Participants:	Participants will be enrolled at PRIZMA Research Center in Moscow, Russia.

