9 STATISTICAL CONSIDERATIONS

9.1 STATISTICAL HYPOTHESES

- Primary Endpoints:

We hypothesize that, compared to MWID who receive a health education control intervention, those who receive the MASLIHAT peer education intervention will have reduced frequency of syringe and other injection equipment sharing, and reduced frequency of vaginal and anal intercourse without a condom 12 months following the intervention. Alternatively, our null hypothesis is that there will be no difference in the effects of MASLIHAT and the health education control intervention on injection and sexual risk behavior of intervention participants 12 months following the intervention.

We hypothesize that, compared to IDU network members of MWID who receive a health education control intervention, IDU network members of MWID who receive the MASLIHAT peer education intervention will have reduced frequency of syringe and other injection equipment sharing, and reduced frequency of vaginal and anal intercourse without a condom 12 months following the intervention. Alternatively, our null hypothesis is that there will be no difference in the effects of MASLIHAT and the health education control intervention on injection and sexual risk behavior of IDU network members 12 months following the intervention.

- Secondary Endpoint(s):

We hypothesize that, compared to MWID who receive a health education control intervention, those who receive the MASLIHAT peer education intervention will have lower incidence of HIV infection and lower incidence of hepatitis C infection 12 months following the intervention. Alternatively, our null hypothesis is that there will be no difference in the effects of MASLIHAT and the health education control intervention on the incidence of HIV or HCV among intervention participants 12 months following the intervention.

We hypothesize that, compared to IDU network members of MWID who receive a health education control intervention, IDU network members of MWID who receive the MASLIHAT peer education intervention will have lower incidence of HIV infection and lower incidence of hepatitis C infection 12

months following the intervention. Alternatively, our null hypothesis is that there will be no difference in the effects of MASLIHAT and the health education control intervention on the incidence of HIV or HCV among IDU network members 12 months following the intervention.

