9.4.2 ANALYSIS OF THE PRIMARY ENDPOINT(S)

Relative frequency of syringe sharing, equipment sharing, and vaginal or anal sex without a condom in the past 3 months will be measured at each time point on a 7-point Likert-type scale (Never, Rarely, Less than half the time, About half the time, More than half the time, Most of the time, Always). We will analyze ordinal outcomes, and we will also dichotomize responses to analyze binary (none/any) outcomes.

We will conduct repeated measures mixed effects regressions with random intercepts for subject and recruitment site to test the effect of intervention condition on changes in the outcome variables. We will use ordinal logistic regression for ordinal outcomes and modified Poisson regression for binary outcomes. We will conduct a test of the proportional odds assumption with a likelihood ratio test comparing the proportional odds model with a non-proportional odds model.⁷⁴ We will include the interaction of time and participant type (intervention participant vs. network member) to test for differential effects. If the interaction term suggests differential effects ($p < .10$), we will stratify analyses by participant type. Sociodemographic characteristics (age, education, time in Moscow) will be included as covariates in the analysis if they are related to the outcome at baseline or if they vary significantly across conditions. All participants with at least one follow-up interview will be included in the analysis.

Dosage: If there is variability in attendance, we will estimate repeated measures mixed effect models predicting outcomes with session attendance and the interaction between time, intervention condition, and session attendance as predictors. A significant interaction effect will indicate that the effect of the intervention is moderated by session attendance.

Social Network Diffusion. Additional analyses among network members will examine associations between exposure to intervention concepts (i.e. conversations about health, drugs/alcohol HIV) and changes in outcomes over time.

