The results of mixed effects ordinal logit models will be reported as odds ratios with 95% confidence intervals, and exact p-values. Predicted probabilities will be computed from the logit model. The results of mixed effects modified Poisson regressions will be reported as relative risk ratios with 95% confidence intervals, and exact p-values. We will also report intra-class correlations for the subject and site (cluster) levels.

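### The interaction that decides whether the primary analysis is split by participant type omits study arm, so it does not test whether MASLIHAT works differently in index men and network members

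*Combined protocol and SAP*

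**What the plan says.** The primary model in 9.4.2 is a repeated-measures mixed model "to test the effect of intervention condition on changes in the outcome variables", with "modified Poisson regression for binary outcomes". Its results are to be given on the ratio scale: "mixed effects modified Poisson regressions will be reported as relative risk ratios".

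For differences between the two kinds of participant, 9.4.2 says: "We will include the interaction of time and participant type (intervention participant vs. network member) to test for differential effects". If that term reaches p<.10, "we will stratify analyses by participant type". Section 9.4.1 uses the same term for outcomes and mediators generally, but without the p<.10 rule.

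The synopsis (1.1) gives the sample as "including 140 intervention participants (70 MASLIHAT, 70 control group) and 280 network members". An intervention participant is therefore an index man in either arm, not a man who received MASLIHAT.

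Section 9.1 states separate primary hypotheses for the two types. The null for index men is of no difference between arms "on injection and sexual risk behavior of intervention participants 12 months following the intervention", and a parallel null covers network members.

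**The concern.** A test of whether the intervention effect differs by type has to involve the intervention. The written term does not contain it. It compares how index men and network members change over time, whichever arm they are in.

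The term also controls a decision. Section 9.4.7 plans no subgroup analyses, so the p<.10 rule is the only stated route to arm effects by type on syringe sharing, equipment sharing and condomless sex. If the rule fails to fire when effects differ, one pooled estimate answers two separate primary hypotheses. The opposite error, stratifying without need, mainly costs precision.

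**Working it through.** **The plan's own figures.** Section 9.2 gives power for the binary outcomes but for no interaction. Inputs for index men are 10 per site, ICC 0.05 and alpha .01 (9.2), with six sites per arm (6.3). The design effect is 1 + 9 x 0.05 = 1.45, so the effective number per arm is 60/1.45 = 41.4. A two-sided normal approximation gives 81.6% for 35% v 5% (plan: at least 80% for condomless sex) and 93.9% for 50% v 10% (plan: over 90% for syringe sharing). The stated power can be reproduced, but it does not bear on the interaction.

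**What the written term estimates.** Let dM and dC be the index-minus-network difference in log change from baseline in the MASLIHAT and control arms.

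- Differential intervention effect: dM - dC (arm x time x type).
- Written term: a weighted average of dM and dC. On the log scale the arm with more events gets more weight. When MASLIHAT works, that is the control arm.

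Four examples, all with 50% at baseline:

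- Flat control, ratios 0.20 index and 0.60 network: dM = ln(0.20/0.60) = -1.10 and dC = 0. The true difference is 1.10 in size; the written term estimates 0.29 to 0.36, depending on whether arm x type is also fitted.
- Flat control, ratios 0.10 and 0.30: again 1.10 in size; the written term estimates 0.17 to 0.25.
- Arm ratios 0.40 and 1.00, network men in both arms falling from 50% to 40%: dM = ln(0.20/0.50) - ln(0.40/0.50) = -0.69 and dC = 0 - ln(0.40/0.50) = +0.22. The true difference is -0.92, but the two parts have opposite signs and partly cancel in the average.
- Equal arm ratio 0.60 in both types, control index men falling from 50% to 40%: dM = dC = -0.22. The true difference is 0; the written term estimates -0.22.

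**How often p<.10 is reached.** From the plan: 63 index and 119 network men per arm (70 less 10% attrition, 140 less 15%). Assumed: 50% baseline, within-man latent correlation 0.3, one follow-up, no site effects. The model is log-link Poisson with subject-robust errors, 20,000 runs (10,000 for the 0.10/0.30 row).

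| Arm risk ratio, index/network | Shared trend | Written | Written + arm x type | Three-way |
|---|---|---|---|---|
| No effect | none | 10% | 10% | 10% |
| 0.40/1.00 | none | 74% | 78% | 86% |
| 0.20/0.60 | none | 53% | 67% | 83% |
| 0.10/0.30 | none | 25% | 38% | 55% |
| 0.40/1.00 | network -5 points | 47% | 53% | 85% |
| 0.40/1.00 | network -10 points | 20% | 24% | 84% |
| 0.40/1.00 | network -15 points | 10% | 11% | 82% |
| 0.60/0.60 | index -10 points | 37% | 36% | 10% |

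The 0.10/0.30 row takes the two ends of the 5% to 15% MASLIHAT range in 9.2. Giving 5% to index men and 15% to network men is an assumption, because 9.2 does not split the range by type. In that row 3.9% of three-way fits had an empty cell and were set aside.

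**What pooling would report.** For 0.20/0.60: (63 x 0.10 + 119 x 0.30)/182 = 0.231, and 0.231/0.50 = 0.46. Network men are 119/182, about two-thirds.

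**Sensitivity** (written / written + arm x type / three-way, %).

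| Setting | 0.40/1.00 flat | 0.20/0.60 flat | 0.40/1.00, network -10 |
|---|---|---|---|
| Site ICC 0.05 added | 74/78/86 | 53/67/82 | 20/25/84 |
| Four follow-ups, one post-baseline term | 91/95/98 | 76/95/99 | 30/42/98 |
| Four follow-ups, categorical time | 75/83/91 | 55/82/93 | 20/28/90 |
| Logit link, one follow-up | 72/73/77 | 49/57/69 | 20/22/77 |

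On risk-difference change scores with a flat control arm the two terms reject equally often (71% v 71% and 44% v 44%). With a 10-point shared network fall they do not (19% v 71%).

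**The case against.** The strongest reply is that arm is implied. Section 9.4.2 does not write out arm x time either; the reader infers it from the stated aim of the model. The same charity, applied to a sentence whose purpose is to find differential effects, would supply the three-way term, and the formal SAP promised in 9.1 could say so. Against this, the dosage paragraph of the same section tests moderation with "the interaction between time, intervention condition, and session attendance as predictors". Where the authors mean moderation of the intervention effect, they name the arm. As written, an analyst would fit the two-way term, and a later SAP would inherit it.

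The second reply concerns size, and much of it stands. The trial has four follow-ups, not one. With a single post-baseline term, wrongful pooling at 0.20/0.60 falls to 24% (5% if arm x type is fitted) against 1%. The result depends on time coding and on whether arm x type is included, and the plan states neither. The type-specific ratios are assumed, the documents give no figure for shared trends, and 9.2 expects little change in controls. The simulations use a marginal Poisson model, not the planned mixed model, and the seven-level ordinal model was not simulated. These points change the size of the illustration; the algebra depends on none of them.

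Third, reporting by type in every case goes further than naming the arm. That is fair: it rests on 9.1 and 9.4.3, not on the missing term. Pooling is also a legitimate analysis, since 9.2 gives power for the complete sample.

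**Conclusion.** The concern holds. The term in 9.4.1 and 9.4.2 averages over arms and cannot test whether the intervention effect differs by participant type, so the p<.10 rule in 9.4.2 rests on the wrong quantity. This is a stated rule that gives a wrong answer, not a missing detail.

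How much it costs depends on the true pattern. With a flat control arm, four follow-ups and arm x type in the model the loss can be small (95% v 99% at 0.20/0.60 with one post-baseline term). It is moderate with one follow-up or categorical time. It is large under any sizeable trend shared by one type across both arms: 30% to 42% v 98% with four follow-ups and a 10-point network fall. These percentages rest on the assumed 50% baseline, within-man correlation and type-specific effects. It should be corrected before the first interim analysis, so that the choice of term cannot depend on the data.

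**What to change.** In 9.4.1 and 9.4.2, replace the term with arm x time x participant type and all its lower-order terms, and carry the same wording into the SAP. From that model, report the 12-month arm effect separately for index men and network members in all cases, as the hypotheses in 9.1 require and as 9.4.3 already does for HIV and HCV. Keep the interaction p-value as descriptive, because even the correct term misses real differences (55% in the 0.10/0.30 case with one follow-up). A pooled estimate can be given in addition.

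The cost is wording and a few model terms; no new data are needed. Intervals by type are wider. In the one-follow-up illustration, before site effects, a risk ratio of 0.60 has a 95% interval of 0.36 to 1.01 for index men, 0.41 to 0.87 for network members and 0.44 to 0.81 pooled. There are two estimates per primary outcome, which adds multiplicity but matches the two hypotheses already stated. Power for index men alone is not assured across the range in 9.2: by the method that gives 82% for 35% v 5%, it is 56% for 35% v 10%. The plan should say so.

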3 OBJECTIVES AND ENDPOINTS

OBJECTIVES	ENDPOINTS	JUSTIFICATION FOR ENDPOINTS	PUTATIVE MECHANISMS OF ACTION
Primary			
Assess the efficacy of the MASLIHAT intervention compared to the TANSIHAT control condition for reducing injection equipment sharing, condomless sex, and heavy alcohol use among intervention participants and among their network members.	Reduce the proportion of men sharing syringes or other injection equipment in the past 3 months to 10% or less; reduce the proportion of men engaging in condomless sex in the past 3 months to 10% or less. Reduce the proportion of men engaging in heavy	Behavioral outcomes are predictive of HIV and hepatitis C infection. Sharing of syringes and other injection equipment is a significant risk factor for HIV and HCV, and condomless sex is a significant risk factor for HIV. Heavy alcohol use increases the	MASLIHAT is a peer education network intervention based on social cognitive theory which suggests that individuals will adopt new norms and practices that reduce their HIV risk by learning how and why they should do so and by observing role

OBJECTIVES	ENDPOINTS	JUSTIFICATION FOR ENDPOINTS	PUTATIVE MECHANISMS OF ACTION
	alcohol use in the past 3 months to 10% or less.	likelihood of risky behavior that leads to infection acquisition, and increases the risk of liver disease associated with HCV.	models to follow. We also draw on Yang's Theory of Migration, which posits that successfully changing risk behavior requires modifying the psycho-social conditions and life circumstance that help to generate it. By transforming their own HIV norms and behavior, and encouraging others at risk to do so too, migrant peer educators can initiate positive changes at the individual and social network levels in both their host country and their home country when they return.
Secondary			
Assess the efficacy of the MASLIHAT intervention compared to the TANSIHAT control condition for reducing the incidence of HIV and hepatitis C infection among intervention participants and among their network members .	Reduce the 12-month incidence of HIV and HCV by 50% compared to the control group.	The risk of HIV and HCV infection will be reduced by changes in individual and peer network behavior.	
Tertiary/Exploratory			

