9.4.3 ANALYSIS OF THE SECONDARY ENDPOINT(S)

Secondary outcomes are HIV and HCV incidence over 12 months. Participants who are HIV antibody positive at baseline will be excluded from the analysis. Participants who are HCV RNA positive at baseline and at 6-months (i.e. chronic infection) will be excluded from the analysis. HCV infection will be operationalized as a positive antibody test following a negative antibody test, or for persons who are AB+ at baseline, a positive HCV RNA test following a negative HCV RNA test. We will conduct a missing data analysis to check for differences between participants with and without test results. If more than 5% of the data are missing we will employ full-information maximum likelihood methods using Mplus.

We will compare incidence rates of HIV and HCV infection between the two intervention conditions among intervention participants, and among network members, with GEE modified Poisson regression to estimate relative risks, adjusted for clustering by recruitment site.⁷⁵ We will estimate the effect of intervention condition, adjusting for covariates including age, education, duration of injection, and length of time in Russia if they are related to the outcome at baseline or if they vary significantly across conditions. The results will be reported as relative risk ratios with 95% confidence intervals, and exact p-values.

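### Section 9.1 states separate primary hypotheses for index men and for network members, but 9.4.2 plans separate arm comparisons only when an interaction pre-test reaches p < .10

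*Combined protocol and SAP*

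**What the plan says.** Section 9.1 states two behavioural null hypotheses, each of no arm difference. One concerns effects "on injection and sexual risk behavior of intervention participants 12 months following the intervention", the other effects "on injection and sexual risk behavior of IDU network members 12 months following the intervention". The primary objective in section 3 likewise covers sharing, condomless sex and "heavy alcohol use among intervention participants and among their network members".

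Section 9.2 computes power for binary outcomes at cluster sizes of 10, 20 and 30, standing for index men, network members and the complete sample.

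Section 9.4.2 then describes one repeated-measures model on all participants. On participant type it says: "We will include the interaction of time and participant type (intervention participant vs. network member) to test for differential effects". The rule follows: "If the interaction term suggests differential effects ($p < .10$), we will stratify analyses by participant type". Nothing is said about separate arm comparisons when the term is not significant.

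For HIV and HCV, section 9.4.3 has no such condition: arms are compared "among intervention participants, and among network members, with GEE modified Poisson regression to estimate relative risks".

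**The concern.** Whether the two primary hypotheses are tested one by one is decided by the data. If the pre-test is not significant, the planned output is one pooled effect. About two-thirds of that effect comes from network men (280 of 420 enrolled), and it answers neither 9.1 hypothesis. Failing to reject an interaction is weak evidence of equal effects, because interaction tests have less power than the comparisons they screen. An effect confined to trained men could be reported as a diluted effect for all, or missed.

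The pre-test also does not ask the right question as written. Time by participant type asks whether index and network men change differently over time, averaged over arms. A difference in the intervention effect needs condition in the term. The conditional rule would remain a problem even with that corrected, so the figures below assume the corrected term.

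**Working it through.** **1. Is a separate arm comparison planned elsewhere?** For the behavioural outcomes, no. Section 9.4.3 covers only HIV and HCV. The diffusion analysis among network members in 9.4.2 relates exposure to outcome, so it is not a randomised comparison. Section 9.4.7 plans no sub-group analyses.

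**2. The plan's own power (9.2).** Inputs: 12 sites, 6 per arm (6.3); ICC 0.05 and alpha .01 (9.2); two-sided tests (9.4.1). The effective number per arm is n = 6m / (1 + (m − 1) × 0.05).
- m = 10: 60 / 1.45 = 41.4
- m = 20: 120 / 1.95 = 61.5

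Power = Φ[(|p1 − p2| − 2.576 √(2p̄(1 − p̄)/n)) / √((p1(1 − p1) + p2(1 − p2))/n)].
- 35% versus 5%, index men: (0.30 − 0.2265) / 0.0815 = 0.90, power 0.816. Network men: 0.956.
- 50% versus 5%: index men 0.990, network men above 0.99.

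This agrees with the stated figures of at least 80% for condomless sex and over 90% for syringe sharing, if those rates are the predicted ones. With a t reference on 10 df, 35% versus 5% gives 0.687 and 0.873. The claim does not hold over the whole range in 9.2: 30% versus 15% in index men gives 0.17.

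**3. How often the pre-test misses a real difference.** After the attrition in 9.2, each arm keeps 70 × 0.90 = 63 index and 140 × 0.85 = 119 network men. Assumptions: one visit, a condition-by-type test at two-sided .10, normal approximation, site effects shared by both groups (so they cancel), and no effect in network men.

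z = (pC − pI) / √[(pC(1 − pC) + pI(1 − pI))/63 + 2pC(1 − pC)/119]

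miss = Φ(1.645 − z) − Φ(−1.645 − z)

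- 35% versus 5%: z = 0.30 / √(0.00437 + 0.00382) = 3.32, miss 5%.
- 40% versus 15%: z = 0.25 / √(0.00583 + 0.00403) = 2.52, miss 19%.

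Miss rates over the rates in 9.2:

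| Control | Index 5% | Index 10% | Index 15% |
|---|---|---|---|
| 30% | 11% | 29% | 52% |
| 35% | 5% | 16% | 34% |
| 40% | 2% | 7% | 19% |
| 50% | <1% | <1% | 3% |

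**4. Other patterns.**
- Equal effects: z = 0, so the test is non-significant in 90% of trials by construction.
- Index men 35% to 5%, network men 35% to 15%: non-significant in 68% (71% in a simulation with 6 sites per arm and ICC 0.05).

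**5. A weaker effect, outside the 9.2 range.** Index men 40% to 20%, network men unchanged: z = 0.20 / √(0.00635 + 0.00403) = 1.96, miss about 38%.

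Over all trials, at two-sided 5% and ICC 0.05:
- Pooled difference 0.20 × 63/182 = 0.069; design effect 1 + (182/6 − 1) × 0.05 = 2.47; power about 14%.
- Index men alone: 0.20 / √(0.40 × 1.475/63) = 2.07; power about 54%. At alpha .01, Φ(2.07 − 2.576) = 31%.

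Within the trials where the pre-test is not significant (simulation with a shared site effect), power is about 15% pooled and about 24% for index men alone. So about 0.38 × 0.24 = 9% of all trials would have a significant index result that the rule leaves unreported.

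**The case against.** The strongest reply is that pooling was planned. Section 9.2 also sizes the complete sample and relies on it for effects smaller than anticipated. The pooled arm effect is a valid randomised comparison. Section 9.4.2 says what happens if the term is significant; it does not forbid separate estimates otherwise. At the large contrasts the sponsor expects, the pre-test would usually detect an effect confined to index men. Section 9.1 also promises a formal SAP before the first interim analysis, which could settle the matter.

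Much of this stands. It shows that the pooled effect deserves a place in the report and that the harm is modest in the favourable part of the 9.2 range. It does not supply the missing tests: the present text plans no arm comparison within either group when the pre-test is not significant. The pooled analysis has a purpose, but it does not test the hypotheses stated in 9.1. A later SAP is the right place for the repair and does not cure the current wording.

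**Conclusion.** The mismatch between 9.1 and 9.4.2 is real and should be corrected before outcomes are compared by arm. Its size depends on assumed effects. With no network effect, the miss rate runs from under 1% to about 52% over the rates in 9.2. With equal effects, about 90% of trials give neither hypothesis its own test. These figures rest on one visit, a normal approximation with only 12 sites, and an interaction term that includes condition.

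Four stronger readings are tempting, and the documents do not support them.
- **That an effect confined to trained men would usually be hidden.** At 35% versus 5% it is missed in about 5% of trials. A miss of 38% needs an index rate of 20%, outside the 5–15% in 9.2.
- **That the rule trades 54% power for 14%.** Those are powers over all trials. Trials with a non-significant pre-test are those where the index effect happened to look small; there the comparison is about 24% with 15%.
- **That chance switching to stratified results in about 10% of trials with equal effects is a further harm.** Those trials report exactly the separate estimates that 9.1 calls for.
- **That diffusion is the trial's central claim.** Network members' behaviour is part of the primary objective, but section 3 lists network penetration and diffusion as tertiary or exploratory.

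**What to change.** Replace the conditional rule in 9.4.2, and carry the change into the formal SAP before the first interim analysis:
- Fit one model with condition by visit by participant type. Always report the 12-month condition effect for index men and for network members as the two 9.1 contrasts.
- State how alpha is shared between the two contrasts, for example by Holm or by testing each at the .01 level used in 9.2.
- Report the pooled effect and the condition-by-type interaction alongside, with neither deciding what else is shown.

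The cost is wording. Each separate interval will be wider than the pooled one, but 9.2 already computes power at the index and network cluster sizes, so on the plan's own approximation no new sample size is needed. The lower figures with a t reference (0.687 and 0.873 at 35% versus 5%) should be kept in view when the alpha rule is chosen.
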